### **8.2 AE Recording**

All Adverse Events volunteered by the Subjects/Patients or elicited by the Investigator must be recorded on the AE forms provided. All serious/severe AEs must be recorded whether or not considered device/treatment related. All device related complications that occur during the study duration and/or malfunctions of study device should be recorded on the AE forms provided. Device complications are defined as those complications relating directly to the functioning of the stimulation system (i.e. IPG, extension or lead).

### **8.3 Reporting AEs**

Throughout the course of the proposed study, all serious/severe adverse events and device related adverse events would be recorded and monitored by the Sponsor and the Investigator. Every effort will be made to remain alert to possible adverse experiences and unexpected findings. If adverse experiences occur, the first concern will be the safety of the subject. Appropriate medical intervention will be made. All completed suicides and suicide attempts (defined by the Columbia Suicide Severity Rating Scale (CSSRS)  $\geq 3$ ) must be reported to the Sponsor immediately (**less than 10 days**) upon discovery. Once the Sponsor is notified of these events, the Sponsor will report these events to the FDA within 10 days.

Individual reports of device related complications will be documented and reported appropriately. The investigator must report all serious AEs to the Sponsor immediately upon discovery by telephone and forward the completed AE form as soon as it is available. The Investigator must also promptly report the resolution to all reported serious or device related AEs.

#### **8.4 Anticipated Adverse Events and Complications**

Implantation of a deep brain stimulation lead is a surgical procedure that may expose the patient to the risks of post-operative pain, stress, or discomfort, intracranial hemorrhage, subcutaneous hemorrhage, intracranial infarctions, venous air embolism (air entering the veins), venous infarctions, symptomatic pneumocephalus (intracranial air causing confusion requiring an extra day stay in the hospital), seizure or convulsions, seroma, infection, aphasia, paralysis, stroke, death, cerebrospinal fluid leakage or abnormality. An additional neurosurgical procedure may be necessary to manage one of the above complications or to replace a fractured lead or to replace the pulse generator

The anticipated adverse events associated with the use of this device may include the following:

- Neuropathy;
- Neuralgia;
- Headache;
- Asthenia, hemiplegia or hemiparesis;
- Cognitive impairment, including confusion, abnormal thinking, hallucinations, alteration of mentation, amnesia, delusions, or dementia;
- Infection;
- Fever;
- Disequilibrium;
- Ataxia;
- Myoclonus;
- Hearing and visual disturbance;
- Paresis;
- Dystonia;
- Attention deficit;
- Dysarthria;
- Sleep disturbance;
- Suicide or Suicide attempt;
- Increase in drug side effects;
- Autonomic instability (change in vital signs);
- Urinary incontinence;
- Worsening depression symptoms (will not be considered an AE);
- Anxiety;
- Ruminativeness;
- Hypomania;

- Mania;
- Panic attacks;
- Obsessive compulsive disorder (OCD) symptoms;
- Psychosis;
- Seizure;
- Apathy;
- Eye disorder;
- Sweating;
- Diarrhea;
- Sensory deficit;
- Drowsiness;
- Difficulty breathing;
- Increased salivation;
- Nausea and/or vomiting;
- Rapid heart rate;
- Pneumonia;
- Skin disorder;
- Edema including periorbital;
- Syncope;
- Persistent pain or redness at the IPG site or the surgery site/extension;
- Pulling sensation along extension site;
- Allergic or rejection response to implanted materials;
- General erosion or local skin erosion over the pulse generator (IPG), burr hole cap, and/or extension;
- Undesirable changes in stimulation possibly related to cellular changes in tissue around the electrodes, changes in the electrode position, or loose electrical connections and/or lead fracture;
- Initial jolt or tingling during stimulation;
- Paresthesia;
- Loss of therapeutic benefit as a result of change in electrode positions, lead fracture, loose electrical connections, DBS system battery failure, DBS system malfunction, or inadvertent turning off of device;
- Lead fracture;
- Lead migration;
- System dislodgement;
- DBS battery failure;
- DBS system malfunction.

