### 2.4 Secondary Variables

- Change from baseline in GAF over time;
- Change from baseline in the MADRS over time;
- Change from baseline in the Hamilton Rating Scale for Depression - 17 item (HRSD-17) over time;
- Change from baseline in the Inventory of Depressive Symptomatology (IDS-C30) over time;
- Change from baseline in Quick Inventory of Depressive Symptomatology (QIDS-SR) over time;
- Change from baseline in the Work and Social Adjustment Scale (WSAS) over time;
- Change from baseline in Patient Global Impression of Severity over time;
- Change from baseline in Clinician Global Impression of Improvement over time;
- Change from baseline in quality of life over time;
- The incidence of all adverse events (i.e. hospitalization due to worsening depression, suicidal ideation or behavior, medical treatment, and device related events) that occur over study duration.
- Change from baseline in Hamilton Anxiety Rating Scale (HAM-A) over time.

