## **8 Adverse Events (AEs)**

### **8.1 AE Definitions**

An ADVERSE EVENT is “Any change, undesired, noxious or pathological in a patient or subject illustrated by signs, symptoms and /or laboratory changes that occur during a clinical trial, whether or not considered drug/treatment related.”

A SERIOUS/SEVERE AE is where the event is/causes:

- Life threatening or fatal
- Requires or prolongs hospitalization
- The patient to be disabled

A DEVICE RELATED AE is an anticipated (those events listed in section 8.4) or unanticipated (those events that occur that are not listed in section 8.4) event that occurs that is considered device related. A device-related event is one that the Investigator feels that the device (i.e. IPG, extension or lead) contributed in any way to the adverse event occurring. A stimulation-related event is one that resolves when stimulation is turned off or turned down.

A NON SERIOUS AE is an event other than one described above.

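### Section 8.4 says without qualification that worsening depression is not an adverse event, which conflicts with 2.4 and 8.1–8.3 for serious or stimulation-related worsening

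*Combined protocol and SAP*

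**What the plan says.** Section 8.4 (Anticipated Adverse Events and Complications) gives a bulleted list of adverse events that may accompany use of the device. One bullet reads "Worsening depression symptoms (will not be considered an AE"). It is the only bullet with an exclusion, and nothing in the visible text limits it by seriousness, hospitalization or cause.

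Four other places bear on the same event:

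- Section 2.4 (Secondary Variables) includes the incidence of all adverse events over the study. Its parenthesis says what is meant: "hospitalization due to worsening depression, suicidal ideation or behavior, medical treatment, and device related events".
- Section 8.1 (AE Definitions) opens its definition with "Any change, undesired, noxious or pathological in a patient or subject illustrated by signs, symptoms". The definition applies whether or not the event is thought treatment related, and it makes no exception for the disease under study. One of its seriousness criteria is "Requires or prolongs hospitalization". It also has a category for effects of stimulation: "A stimulation-related event is one that resolves when stimulation is turned off or turned down".
- Section 8.2 (AE Recording) states: "All serious/severe AEs must be recorded whether or not considered device/treatment related".
- Section 8.3 (Reporting AEs) has the investigator telephone every serious adverse event to the sponsor immediately.

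Section 11 appoints a DSMB to review all serious adverse event data.

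**The concern.** Worsening of the illness under treatment is a plausible harm of a brain-stimulation device, and sections 2.1 and 9.1 place safety in the primary objective. An investigator whose patient is admitted for worsening depression, without suicidality, finds 2.4 counting the admission and 8.4 saying the worsening is not an adverse event. With up to 20 sites, both practices could arise within one trial.

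If sites follow 8.4 literally, such events are missing from the incidence in 2.4, from telephone reporting under 8.3, and from what reaches the DSMB as serious events. The effect would fall on the safety count alone. Worsening is still measured as efficacy through MADRS and the other scales, and under 7.4 a rescue for a 25% MADRS worsening is a treatment failure. Neither route generates a serious adverse event report, and 7.4 assigns rescued worsening no adverse event status.

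**Working it through.** No arithmetic applies, because the plan gives no figure for this point. The check is to trace test cases through the sections.

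**Case A: a patient is hospitalized for worsening depression, with no suicidal ideation or behavior.**

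1. Under 2.4, the hospitalization is named in the adverse event incidence, so it is counted.
2. Under 8.1, worsening is an undesired change shown by symptoms, so it meets the general definition. Because it required hospitalization, it is serious.
3. Under 8.2 it is recorded, and under 8.3 it is telephoned to the sponsor. Under 11 it is part of the data the DSMB reviews.
4. Under 8.4 read literally, worsening depression symptoms are not an adverse event. The duties in 8.2 and 8.3 attach only to adverse events, so steps 1 to 3 do not start.

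The two routes give opposite answers for the same patient.

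**Case B: worsening that the investigator judges stimulation-related, with the device working as programmed.**

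1. Section 8.1 has a category for this, namely an event that resolves when stimulation is turned off or down.
2. Section 8.1 also says "A DEVICE RELATED AE is an anticipated (those events listed in section 8.4") or unanticipated event considered device related. Worsening is on the 8.4 list, so once judged device related it would be sorted as anticipated.
3. The same line of 8.4 says it is not an adverse event at all.
4. Section 8.2 adds "All device related complications that occur during the study duration and/or malfunctions of study device should be recorded on the AE forms provided". However, it defines device complications as those relating directly to the functioning of the IPG, extension or lead. That does not clearly reach worsening caused by stimulation delivered as intended.

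Under 3.1 the control group has no active stimulation for the first 6 months. Worsening truly caused by stimulation can therefore arise only in the active group during the blinded comparison.

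**Cases that other text covers.**

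| Event | Where it is covered |
|---|---|
| Suicide or suicide attempt | Own item in 8.4; own reporting rule in 8.3 |
| Suicidal ideation or behavior | Named in 2.4; own rescue route in 7.4 |
| Lost benefit from lead fracture, battery failure, malfunction or accidental switch-off | Own item in 8.4 |
| Device malfunction or complication | 8.2 |
| Symptom change meeting no seriousness criterion and not attributed to device or stimulation | Rating scales in 2.4 |

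Two cases are left without a clear rule: serious worsening without suicidality, and worsening judged stimulation-related. The explicit event criteria in section 13 concern intracranial hemorrhage, suicides and suicide attempts, so they do not cover either case.

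**The case against.** The strongest reply is that the sections refer to different things. Section 8.4 excludes symptoms, and 2.4 counts a hospitalization that follows from them. Section 8.4 never mentions hospitalization, and it lists suicide and suicide attempt separately, which suggests its drafters already distinguished symptoms from their grave consequences. On that view, 2.4 settles Case A, and 8.1 to 8.3 supply seriousness, recording and reporting. This reading is coherent and may well be what was intended. It does not remove the problem, because no visible sentence adopts it and it leaves Case B unanswered.

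A second reply is that the rule would normally sit in material that cannot be seen. The figure in 8.5 (AE Classification) is not shown, 9.7.1 is redacted, 9.7.2 and the case report forms appear only as headings, and the DSMB plan is a separate document. This stands as a real limit. Even if the rule exists there, 8.4 as worded should point to it.

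Third, treating ordinary symptom change as efficacy rather than as an adverse event is a legitimate design choice. That is accepted; the point does not challenge it.

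Two stronger readings are tempting. A reader might infer that the plan removes serious worsening from the safety data. The documents do not support that: 2.4 names the hospitalization expressly, and a consistent reading is available. A reader might also infer that the 8.4 list decides whether an event is device related. It does not. Section 8.1 leaves relatedness to the investigator's judgment and uses the list only to sort device-related events into anticipated and unanticipated.

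**Conclusion.** The unqualified exclusion in 8.4 conflicts with 2.4 and with 8.1 to 8.3, and the visible text does not resolve the conflict. It is an ambiguity that sites could apply in either direction. It does not show that the plan intends to leave these events out.

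The exposure is confined to two cases: serious worsening without suicidality, and worsening judged stimulation-related. For those, a literal reading of 8.4 would lower the recorded adverse event incidence and thin the serious event data that the DSMB reviews. Efficacy data on worsening are unaffected.

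The size cannot be stated. The documents give no hospitalization rate and no rate of stimulation-related worsening. The number of items on the 8.4 list, or the effect of one missing event on an arm's percentage, would say nothing about how many events are at risk.

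The conclusion assumes that the material not visible does not already hold the rule. If it does, only a cross-reference is missing.

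**What to change.** Reconcile 8.4 with 2.4 and 8.1 to 8.3. Replace the parenthesis in 8.4 with wording such as: *not recorded as an AE if it meets no seriousness criterion in 8.1 and is not judged device- or stimulation-related; such change is captured by the rating scales. Worsening that meets a seriousness criterion, including hospitalization, or is judged device- or stimulation-related is recorded and reported as an AE or SAE under 8.2 and 8.3.*

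If 8.5, the adverse event form, 9.7 or the DSMB plan already states this, a cross-reference in 8.4 is enough.

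The cost is one line of protocol text, a few more AE and SAE forms, and slightly higher reported adverse event rates. The change concerns recording and reporting only; rescue, patient care and device management stay as they are.

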## 8.5 AE Classification

[figure not shown]
Each adverse event will be classified by the Investigator and reported to the Sponsor using the Adverse Event Form of the patient's Case Report Form.

## **9 Data Analysis and Statistical Plan**

### **9.1 Statistical Plan**

The study design for this investigation is a prospective, double-blind, randomized, and controlled study. The primary objective is to demonstrate the safety and efficacy of using subgenual white matter (Brodmann Area 25WM) deep brain stimulation as an adjunctive treatment for Major Depressive Disorder, single or recurrent episode.

### **9.2 Sample Size**

### **9.3 Datasets**

### **9.4 Primary Effectiveness Analysis**

**9.5 Secondary Effectiveness Analyses**

[REDACTED]

[REDACTED]

[REDACTED]

[REDACTED]

[REDACTED]

[REDACTED]

## 9.6 Other Analyses

[REDACTED]

[REDACTED]

[REDACTED]

[REDACTED]

[figure not shown]
## 9.7 Safety Analyses

### 9.7.1 Primary Safety Analysis

[REDACTED]

[figure not shown]

### **9.7.2 Other Analyses of Safety**

### **9.8 Stopping Rule for Futility**

The futility analysis will be done when 75 to 100 patients have achieved the primary endpoint by either completing their Month-6 visit or have terminated from the trial prior to their Month 4 visit. No more than 125 patients will be enrolled into the trial until the results of the futility analysis have been completed and reviewed by FDA.

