### 2.3 Primary Variable

Primary Efficacy: Change from Baseline (defined as mean of 3 Montgomery and Asberg Depression Rating Scale (MADRS) scores) to the mean of months 4, 5, and 6 between treatment groups.

The primary endpoint will be defined as at least a 40% reduction in MADRS and no worsening in Global Assessment of Functioning (GAF).

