**Rescue medications:**

The study psychiatrist should first identify a need for a rescue based on his/her clinical judgment of worsening depression. In the event that a patient needs to be “rescued” due to a severe worsening of their depression (defined as patients who score 25% worse than their baseline average on the MADRS or worsening of suicidal ideation), prior to the completion of 6 months in the study, appropriate intervention may be initiated at the principal investigator’s discretion considering the protocol-specified guidance. The following guidance should be adhered to when the rescue protocol is initiated:

If a patient is rescued based on a 25% worsening of their MADRS score compared to the average MADRS Scores:

- The patient will be considered a treatment failure.
- The visit will serve as the patient’s endpoint data and the patient will be exited from the study. All end-of-study procedures should be performed.
- At the principal investigator discretion, medications may be added or changed as deemed in the best medical interest of the patient.
- Patients who were in either the control group or received active stimulation should enter a separate open-label protocol for long-term follow-up.

If a patient is rescued based on a worsening of suicidal ideation

- A patient who shows imminent suicidal intent but does not attempt suicide will be treated for the acute exacerbation of their symptoms. If the event can be treated with an acute intervention (less than 7 days) then the patient should resume participation in the trial and not be unblinded as to treatment.
- After the acute intervention, the patient must have a MADRS item 10 score of less than 5 to resume participation in the trial.
- After the acute intervention, the patient must resume their previous medication regimen if medications were changed.
- Patient’s medications must be stable for a minimum of 7 days prior to an effectiveness visit
- If the patient attempts suicide, or requires a long-term medication change he/she will be considered and followed as a treatment failure.

Patients who were in either the control group or received active stimulation should enter a separate open-label protocol for long-term follow-up.

At any time during the study the patient feels suicidal or in any danger from worsening depressive symptoms, they, or their caretaker should call their study psychiatrist immediately.

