## 10 Withdrawal of Subjects from Study

Subjects may be discontinued from the study for non treatment-related reasons only when no other option is possible. Reasons for discontinuation include, but are not necessarily limited to:

- Voluntary withdrawal from the study by the subject;
- Subject has moved from the area and is determined to be lost-to-follow-up;
- Investigator may discontinue the Subject's participation in the study for reasons including, but not limited to: subject noncompliance, unwillingness or inability to cooperate with study requirements (therapy regimen, follow-up visits, study determination, etc...).

The reason for discontinuation will be recorded on the appropriate case report form.

Prior to discontinuing a subject, every effort should be made to contact the subject in an effort either to get the subject back into compliance with the protocol, or to obtain as much follow-up data as possible. If a subject decides to discontinue from the study, the subject shall have the option of having the system surgically removed followed by normal psychiatric care. Once the patient exits the study, the device will be turned off (no matter what the randomized treatment was assigned). The device can only be reactivated by the study psychiatrist after the patient enters a separate open-label protocol for long-term follow-up. The patient must sign a separate informed consent and must satisfy the inclusion criteria of the long-term follow up study prior to being enrolled. The study psychiatrist must also deem the subject fit to begin or continue with stimulation.

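### Does the futility count in 9.8 go wrong because it skips patients who exit between Months 4 and 6?

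*Combined protocol and SAP*

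**What the plan says.** Section 9.8 (Stopping Rule for Futility) schedules the look for when "75 to 100 patients have achieved the primary endpoint". In context this means a settled endpoint status, not a response. It names two ways to get there: "completing their Month-6 visit or have terminated from the trial prior to their Month 4 visit". It adds a brake: "No more than 125 patients will be enrolled into the trial until the results of the futility analysis" are complete and FDA has reviewed them.

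Section 7.4, under Rescue medications, covers rescue "prior to the completion of 6 months in the study", so Months 4 to 6 are included. For rescue on a 25% MADRS worsening it says: "The patient will be considered a treatment failure". The rescue visit then supplies the "endpoint data and the patient will be exited from the study".

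Section 2.3 measures the change from baseline "to the mean of months 4, 5, and 6 between treatment groups", which probably explains the Month 4 cut in 9.8. Section 10 intends other exits to be rare: "Subjects may be discontinued from the study for non treatment-related reasons only when no other option is possible". Sections 9.2 to 9.4 show headings only and 9.5 to 9.7.1 are blacked out, so neither the analysis sets nor a futility threshold can be read.

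**The concern.** Read literally, 9.8 leaves a hole between its two routes. A patient rescued for a 25% worsening at Month 3 has terminated before Month 4 and counts at once. The same patient rescued at Month 5 is just as clearly a failure under 7.4, with endpoint data and no further visits to come, yet never enters the count.

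Two things could be at stake. First, enrolment may not pass 125 of the planned 201 until the look is done and reviewed, so a count that runs slow could hold up the trial. Second, if the counted patients were also the ones analysed, known late failures would be left out while early ones were included. That would raise the apparent response rates and could distort the active-control difference on which a futility decision rests.

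**Working it through.** **Which patients fall in the hole.** The contradiction with 7.4 is exact for one route only: rescue on a 25% MADRS worsening, which brings failure status, endpoint data and exit together. After rescue for suicidal ideation with an acute intervention of under 7 days, the patient resumes and can be counted at Month 6. After a suicide attempt or a long-term medication change, the patient is followed as a failure; that bullet does not itself state exit. Ordinary withdrawals between Months 4 and 6 are uncounted too, but the visible text gives them no outcome, so 9.8 contradicts nothing there.

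**Inputs.** From the documents: count C = 75 to 100, cap 125, allocation 2:1. Assumed, because the documents give no figures: the share u of patients exiting between Months 4 and 6, accrual of 5 to 8 per month, and response of 40% active against 20% control.

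**1. The sentence as a clock.** When the count reaches C, the patients with a settled status number C/(1 − u), so C/(1 − u) − C are uncounted. The delay against counting them is that number divided by monthly accrual.

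| u | Uncounted, C = 75 | Uncounted, C = 100 | Delay, months |
|---|---|---|---|
| 2% | 75/0.98 − 75 = 1.5 | 100/0.98 − 100 = 2.0 | 1.5/8 = 0.2 to 2.0/5 = 0.4 |
| 5% | 75/0.95 − 75 = 3.9 | 100/0.95 − 100 = 5.3 | 3.9/8 = 0.5 to 5.3/5 = 1.1 |
| 10% | 75/0.90 − 75 = 8.3 | 100/0.90 − 100 = 11.1 | 8.3/8 = 1.0 to 11.1/5 = 2.2 |

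The plan itself leaves 100 − 75 = 25 patients of latitude, or 25/8 = 3.1 to 25/5 = 5.0 months of accrual. Every entry is smaller than that.

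**2. Can the cap block the look?** At most 125(1 − u) of the first 125 patients can be counted. This equals 100 at u = 20% (125 × 0.80) and 75 at u = 40% (125 × 0.60). Below 20%, either end of the range can be reached.

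**3. If the counted patients were also the interim set.** The visible text does not say this. Suppose it holds and every exit is a failure. The response rate among counted patients is then p/(1 − u), and with equal u the difference becomes 20/(1 − u) points: 20.4, 21.1 and 22.2 at u = 2%, 5% and 10%, so +0.4, +1.1 and +2.2. With no true effect the two rates inflate alike and the difference stays at zero.

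This ignores that early failures enter the count before completers enrolled at the same time, which pulls the other way. A simulation covers both effects: 10% exits before Month 4, exit times uniform within each window, 2:1 blocks of 3, enrolment capped at 125, 4,000 trials per setting, Monte Carlo error about 0.15 to 0.18 points. The comparator is the cohort past its Month-6 date. The standard errors are √(0.24/50 + 0.16/25) = 10.6 points at 75 patients and √(0.24/66.7 + 0.16/33.3) = 9.2 points at 100.

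| Late exits, active/control | Shift in difference, points | In standard errors |
|---|---|---|
| 2%/2% | −0.5 to 0.0 | under 0.05 |
| 5%/5% | +0.2 to +0.7 | under 0.1 |
| 10%/10% | +1.3 to +1.8 | 0.1 to 0.2 |
| 2%/6% | −1.3 to −0.8 | about 0.1 |
| 6%/2% | +1.2 to +1.7 | 0.1 to 0.2 |
| 15%/5% | +4.8 to +5.6 | 0.5 to 0.6 |

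Only the last row is sizeable, and nothing in the documents points to such an imbalance. All rows overstate the part due to the conflict with 7.4, since rescues for a 25% worsening are only a subset of late exits.

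**The case for a change.** The strongest case for acting is that this look gates enrolment, so its trigger should be unambiguous before interim data exist. Otherwise someone must decide mid-trial whether a Month-5 rescue counts, and one sentence would settle it. The Month 4 to 6 averaging window explains why early exits count at once, but not how a known failure inside the window is treated.

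The textual point stands: 9.8 does not say that the rescue visit takes the place of Month 6. The consequence does not follow. Section 7.4 makes that visit the source of the endpoint data and asks for the end-of-study procedures, so an analyst would naturally treat the patient as having a settled endpoint. Either reading can be applied to the pooled count without knowing treatment arms. The plan already allows the look anywhere from 75 to 100, so uncertainty over a few patients adds no real freedom.

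The available rewrites bring no clear gain either. A trigger based on the scheduled Month-6 date would, under the same assumptions, move the look 0.3 to 0.4 months later with no late exits, 0.1 to 0.7 months earlier at 5%, and 0.6 to 1.9 months earlier at 10%. It would also prescribe an interim set without sight of 9.3 and 9.4. Counting every exit at once closes the hole but puts failures further ahead of completers. At 2% late exits it shifts the difference by −0.4 to −0.8 points, no better than −0.5 to 0.0 under the written count. Any change would also need the amendment approvals in section 12.

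**Conclusion.** No change follows. Sections 9.8 and 7.4 do not mesh perfectly for a patient rescued on a 25% MADRS worsening between the Month 4 and Month 6 visits. This is a gap in wording that analysts can fill sensibly from 7.4. The visible sentence fixes the timing of the look and not its analysis set, so no bias in the futility result is shown.

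The timing effect is about 2 to 11 patients at assumed late-exit rates of 2% to 10%, within the plan's own 25-patient latitude, and the cap of 125 does not bind below 20%. On the less favourable reading, where the counted patients are the ones analysed, the shift is 0.2 standard errors or less unless late exits differ strongly by arm. No change in the probability of stopping can be calculated, because no threshold is visible. The sizes rest on assumed exit, accrual and response rates; the conclusion that the sentence is a clock rests on its visible wording.
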